**Table 2. Censoring Rules for Duration of Response**

DOR	Events	Censoring
Primary	
 
• Deterioration from best response
 
• Initiation of new systemic therapy for cGVHD
 
• Death
 
	
 
• Last documented response assessment
 
• If LR or initiation of new systemic therapy happens immediately after two or more missed response assessments, the event date should be set as four weeks (one cycle) after last documented response assessment prior this event
 

Secondary	
 
• Documented LR
 
• Initiation of new systemic therapy for cGVHD
 
• Death
 
	
Tertiary	
 
• Initiation of new systemic therapy for cGVHD
 
• Death
 
	Last response assessment or long term follow up assessment, whichever is the latest and available
Quaternary	
 
• Documented LR
 
• Initiation of new systemic therapy for cGVHD
 
• Death
 
 
With summation of DOR from multiple episodes
	Same with censoring rule for primary and secondary

cGVHD = chronic graft versus host disease; DOR = duration of response; LR = lack of response

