6.3. Overview of Study Design

This is a Phase 2a, dose-escalation, open-label study designed to evaluate the safety, tolerability, and activity of KD025 in subjects with steroid-dependent cGVHD and active disease in terms of PR and CR as defined by the 2014 NIH Consensus Development Project on clinical trials in cGVHD (see [Appendix B](#)). This study also is designed to use the Physician-reported global cGVHD Activity Assessment to evaluate cGVHD severity; use the cGVHD Activity Assessment Patient Self-Report to assess symptom activity (see [Appendix C](#)); evaluate FFS; evaluate OS; assess changes in corticosteroid and calcineurin inhibitor (CNI) dose; evaluate TTNT; and assess the PK of KD025 in subjects with cGVHD. Changes in symptom burden/bother will be documented using the Lee cGVHD Symptom Scale (see [Appendix D](#)). Changes in the expression of several cytokines (including IL-17A, IL-21, and IL-2) in plasma and percentages of immune-cell subtypes (including Th17 and Treg cells) in whole blood after KD025 administration to subjects with cGVHD.

Subjects who have signed an IRB/IEC-approved informed consent form, and met all of the inclusion/exclusion criteria ([Section 7.2](#) and [7.3](#)), will be enrolled. Approximately 48 subjects will receive orally administered KD025 200 mg QD (n = 16), KD025 200 mg BID (n = 16), or KD025 400 mg QD (n = 16). Study drug will be administered in 28-day cycles until disease progression or unacceptable toxicity occurs. For disease progression, subjects with a “Lack of Response (LOR) – Mixed” response assessment ([Appendix B](#)) may continue treatment with KD025 and remain on study if the investigator considers continued treatment to be in the subject’s best interest, only after approval from the medical monitor and documentation of the subject’s willingness to continue. Subjects may receive study drug treatment either in the inpatient or outpatient setting.

Prior to enrolling subsequent cohorts, the safety data in each previous cohort will be evaluated after 8 subjects have reached 2 months of treatment to assure there is no safety signal. As this is an open-label study, safety data will be continuously monitored. If $\geq 25\%$ of subjects in a cohort experience a [Common Terminology Criteria for Adverse Events \(CTCAE\)](#) v4.03 Grade 2 liver toxicity or a CTCAE v4.03 Grade 3 (or higher) AE in the same organ or body system, or if

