> 25% of subjects in a cohort are discontinued for toxicity that persists for 14 days, then dose escalation to the next cohort will not occur, and all subjects in that dose cohort will be dose reduced.

If \geq 25% of subjects in the 200 mg QD cohort experience a CTCAE v4.03 Grade 2 liver toxicity or a CTCAE v4.03 Grade 3 (or higher) AE in the same organ or body system, or if > 25% of subjects in a cohort are discontinued for toxicity that persists for 14 days, then further dosing will not occur and the study will be terminated. See [Section 14.4](#) for additional information.

Response criteria will be assessed on Day 1 of each cycle starting at Cycle 2 Day 1 visit as well as the end of treatment (EOT) visit using the criteria of 2014 NIH Consensus Development Project on Clinical Trials in cGVHD (CR, PR, and Lack of Response (unchanged, mixed, or progression); [Lee et al., 2015](#)). cGVHD severity (clinician reported) and symptom (subject reported) assessments will be performed on Day 1 of each cycle starting on Cycle 1 Day 1 as well as the EOT visit using the Physician-reported global cGVHD Activity Assessment form ([Appendix A](#)), cGVHD Activity Assessment: Patient Self Report, and Lee cGVHD Symptom Scale (see [Appendices C and D](#)).

At Cycle 25, Day 1 (C25D1), and all odd cycles thereafter (ie, C27D1, C29D1, C31D1, etc.), subjects will receive 2 cycles worth of study drug along with 2 diaries and will return to the clinic at the next odd cycle for assessments and IP accountability. Investigators and/or subjects have the option of coming into the clinic at one or more even cycles (i.e., C26D1, C28D1, C30D1, etc). On even cycles, when patients do not come to clinic, the study staff will contact the patient via phone and document any new adverse events and concomitant medications.

Subjects will also undergo assessments as described in [Table 1](#).

Table 1: Study Assessments

Assessments	Screen ⁿ	Treatment Period (Each Cycle is 4 Weeks)							EOT ^{q,t}	28-Day Follow-Up (±7 days) ^r	UNS ^s	Long-Term Follow-Up
		Cycle 1					Cycle 2 and Beyond ^{o,p}					
		-29 to -1	1	2	8 (±3 days)	15 (±3 days)	22 (±3 days)	1 (±3 days)				
Informed consent	X											
Medical history/Demographics	X											
Physical examination ^a	X	X		X	X	X	X		X	X	X	
Vital signs ^b	X	X		X	X	X	X		X	X	X	
Karnofsky Performance Scale score	X	X		X	X	X	X		X	X	X	
Hematology and chemistry	X	X		X	X	X	X		X	X	X	
TSH	X						X		X	X	X	
Urinalysis	X						X		X	X	X	
Virology ^c	X											

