8.4.3 Cycles 2 and Beyond, Day 1 (± 3 days)

On Day 1 of Cycles 2 and beyond, subjects will come to the clinic to have the following procedures completed:

- Complete PE, including weight
- Seated vital sign measurements (sitting blood pressure, pulse, respiratory rate, temperature)
- Karnofsky Performance Scale score
- Clinical laboratory tests (hematology and serum chemistry panel)
- TSH
- Urinalysis
- Supine 12-Lead ECG; pre-dose on Day 1 of Cycle 4 and Cycle 7 only; to be performed 3 times consecutively within 30 minutes (must have an interval of at least 1–2 minutes between ECGs)
- Urine pregnancy test (for women of childbearing potential. Positive results are to be confirmed with serum testing.)

- Pulmonary function tests (including FEV₁, FVC, DL_{CO}, TLC, and RV; to be performed every other cycle, starting with Cycle 3 for subjects without lung involvement)
- PK sample collection (Cycle 2 only at the following time points: pre-dose [Time 0], and 1, 2, 3, 4, 5, and 6 hours after dosing [after first dose for subjects in the BID group]); a pre-dose sample is to be collected at the Cycle 4 and Cycle 7 visit
- PD blood sample collection (Cycles 2, 4, and 7 only: pre-dose)
- Study drug administration
- Dispense/Collect study drug
- Collect study drug diary
- Response assessment.
- Physician-Reported Global cGVHD Activity Assessment
- cGVHD Activity Assessment - Patient Self Report
- Lee cGVHD Symptom Scale
- Concomitant medications assessment
- AE assessment

At Cycle 25, Day 1 (C25D1), and all odd cycles thereafter (i.e., C27D1, C29D1, C31D1, etc.), subjects will receive 2 cycles worth of study drug along with 2 diaries and will return to the clinic at the next odd cycle for assessments and IP accountability. Investigators and/or subjects have the option of coming into clinic at one or more even cycles (i.e., C26D1, C28D1, C30D1, etc). On even cycles, when patients do not come to clinic, the study staff will contact the patient via phone and document any new adverse events and concomitant medications.

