## **3.8 Endpoints for Activity Analysis**

### **3.8.1 Primary Endpoint**

The overall response rate (ORR) is the primary endpoint of the study.

The ORR is defined as the proportion of subjects meeting the overall response criteria assessment of CR or PR at any post-baseline response assessment.

The overall response determination of cGVHD is based on the cGVHD response assessment performed by clinicians as per the 2014 NIH Consensus Development Project for Clinical Trials in cGVHD criteria. The overall response is defined using the scores from 9 organs (skin, eyes, mouth, esophagus, upper GI, lower GI, liver, lungs, and joints and fascia; see [Appendix B](#)) plus global severity rating. The results of overall response at each assessment time point are evaluated by investigator and categorized as CR, PR, or Lack of Response (LR), where LR includes the response status of unchanged, mixed, or progression.

If a treated subject does not have any response assessment, this subject will be counted as a non-responder.

The ORR and its two-sided 95% CI using Clopper-Pearson method will be presented.

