### **3.8.2 Secondary Endpoints**

#### **3.8.2.1 Duration of Response (DOR)**

The primary definition of DOR is the time from first documentation of response to the time of first documentation of deterioration from best response (e.g., CR to PR, or PR to LR).

The secondary definition of DOR is the time from first documentation of response to the time of first documentation of lack of response.

The tertiary definition of DOR is the time from first documentation of response to the time of initiation of new systemic cGVHD therapy (which will be defined by clinical team review).

The quaternary definition of DOR is the time from first documentation of response to the time of first documentation of lack of response (as the secondary definition) but with durations summed for multiple response/lack of response episodes.

The DOR will be reported only for responders and statistics will include:

- Kaplan-Meier plots and descriptive statistics of DOR. The censoring rules in [Table 2](#) will be applied
- Landmark analyses: Number and percentage of subjects with response sustained for  $\geq 12$ ,  $\geq 20$ ,  $\geq 24$ ,  $\geq 32$ ,  $\geq 36$ , and  $\geq 48$  weeks

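### SAP Table 2 re-dates LR and new therapy after missed assessments but not CR-to-PR deterioration, so the same gap gives primary DOR values at least 8 weeks apart; its fixed 4-week offset also does not fit the visit schedule from Cycle 25

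*SAP*

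**What the plan says.** SAP 3.8.2.1 ends primary DOR at "first documentation of deterioration from best response (e.g., CR to PR, or PR to LR". Table 2 lists three events for it: deterioration from best response, start of new systemic cGVHD therapy, and death.

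For events found after a gap, Table 2 has this rule: "If LR or initiation of new systemic therapy happens immediately after two or more missed response assessments, the event date should be set". The date that it then assigns is fixed, whatever the visit interval: "as four weeks (one cycle) after last documented response assessment prior this event". The rule serves primary and secondary DOR, and the quaternary row refers back to it. Tertiary DOR has its own censoring rule with no such re-dating.

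SAP 3.8.1 defines the response categories, "where LR includes the response status of unchanged, mixed, or progression". A PR is therefore not LR.

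On timing, Protocol 6.3 says "Study drug will be administered in 28-day cycles until disease progression or unacceptable toxicity occurs" and "Response criteria will be assessed on Day 1 of each cycle starting at Cycle 2 Day 1 visit". From Cycle 25 the required clinic visits fall on odd cycles, and even-cycle visits are optional. Protocol 8.4.3 adds: "On even cycles, when patients do not come to clinic, the study staff will contact the patient via phone", to record adverse events and concomitant medications.

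**The concern.** The event list and the re-dating rule do not match. A complete responder who returns from a gap in PR has had a primary-DOR event, but the rule does not reach it. The event stays at the visit where it was found, and the whole unassessed gap counts as response. A subject who returns in LR after the same gap is moved back to four weeks after the last assessment. Primary DOR then depends on which event ended the gap as well as on how long response was documented.

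No other text resolves this. The SAP's rule on missing event dates (3.1.5) applies only when the day of a date is missing.

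The offset is a second, separate matter. Four weeks equals one assessment interval only while visits are 4-weekly. From Cycle 25 the required interval is twice that.

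Primary DOR is reported as a Kaplan-Meier curve and as landmark percentages at 12 to 48 weeks. The SAP's document history shows that DOR definitions were added after a regulatory meeting and that DOR censoring was revised again in version 2.1. Exact dating therefore matters to the sponsor.

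**Working it through.** **Inputs.** Cycle length 28 days (Protocol 6.3). Required assessment interval *s*: 4 weeks before Cycle 25, 8 weeks from Cycle 25 (Protocol 6.3, 8.4.3). Trigger: at least two missed assessments, ending in LR or new therapy (SAP Table 2). Assigned date: last assessment + 4 weeks. Visit windows of ±3 days are ignored.

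**The plan's own figure.** 28 / 7 = 4 weeks, so the equation of four weeks with one cycle is reproduced, and up to Cycle 25 it is also one assessment interval.

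**Formula.** With *m* consecutive missed assessments, the event is seen at last + *s*(*m* + 1). For *m* ≥ 2, LR is dated last + 4, while CR-to-PR keeps last + *s*(*m* + 1). The difference is *s*(*m* + 1) − 4 weeks.

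| *s* (weeks) | *m* | LR dated | CR-to-PR dated | Difference (weeks) |
|---|---|---|---|---|
| 4 | 1 | last+8 (rule not triggered) | last+8 | 0 |
| 4 | 2 | last+4 | last+12 | 8 |
| 4 | 3 | last+4 | last+16 | 12 |
| 8 | 2 | last+4 | last+24 | 20 |

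**Landmarks.** Suppose response was last documented 12 weeks after first response, weeks 16 and 20 were missed, and the event was seen at week 24. With LR, DOR = 12 + 4 = 16 weeks, which fails the 20- and 24-week landmarks. With CR-to-PR, DOR = 24 weeks, which meets both. At the planning response rate in Protocol 17.2, a cohort has about 0.25 × 16 = 4 responders, so one record that crosses a landmark would move that cohort's percentage by 1/4 = 25 points. This is an illustration, since the documents show no such record.

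**Offset from Cycle 25.** Cycle 25 Day 1 is 24 × 4 = 96 weeks after Cycle 1 Day 1. If the last assessment is at Cycle 25, two odd-cycle visits are missed and LR follows, the rule dates LR at last+4 (week 100). The first missed required visit is at last+8 (week 104). A DOR dated at week 100 falls below the longest landmark, 48 weeks, only if response began after week 100 − 48 = 52. For most responders this touches only the late part of the curve.

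**Death.** After two missed 4-week assessments, a death before the next visit falls more than 8 and up to 12 weeks after the last assessment. It differs from the LR date by more than 4 and up to 8 weeks.

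**After the change.** CR-to-PR and LR after the same gap are both dated last+4 on the 4-week schedule and, after an odd-cycle assessment from Cycle 25, last+8. The difference between them is 0.

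**The case against.** Much can be said for leaving the table alone, and several of these arguments limit the point.

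- **The omission may be deliberate.** A subject who returns in PR has a documented response on both sides of the gap, and the SAP never states the purpose of the rule. This would be a good argument for secondary DOR, where PR is not an event. It does not fit primary DOR, which counts the step from CR to PR as the end of response. The SAP gives no reason to date that step differently from LR.
- **Long gaps should be rare.** The protocol dispenses one month of drug (14.7), or two cycles from Cycle 25 (8.4.3). It discontinues subjects who skip more than 7 consecutive days (14.3) or need pauses of more than 14 days (14.4). After discontinuation, no monthly response assessments are scheduled. This stands. What remains is mainly attended visits without a response assessment, or drug supplied without a visit.
- **Death is observed on its own date.** Keeping that date is defensible, and back-dating it to a time when the subject was alive is debatable. The start of new therapy is also a dated event, however, and the rule does move it. The plan should state its choice for death.
- **The endpoint is secondary and descriptive** in a study the SAP calls exploratory, and SAP Table 5 lists every DOR episode by subject. This limits severity but does not supply the missing rule.

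A reader might also infer that a single missed clinic visit after Cycle 25 triggers the rule, because the skipped even cycles on either side would count as missed too. Protocol 6.3 does still speak of assessment on Day 1 of each cycle. But it makes even-cycle visits optional, and an option not taken is hardly a missed assessment. The SAP should say so, but that reading is not the plan's natural meaning.

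**Conclusion.** The point holds for primary DOR. After two missed 4-week assessments, CR-to-PR is dated 8 weeks later than LR, and after three, 12 weeks later. It applies only to subjects whose best response is CR and who return in PR. The number of such records is unknown and probably small. ORR is not affected, nor are the other three DOR definitions by this omission. The mismatch of the 4-week offset with the 8-week interval from Cycle 25 is real but separate, and mainly concerns the late Kaplan-Meier curve.

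Three stronger readings are not supported:

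- It would be wrong to say that complete responders with missed visits in general get longer DOR. Those who return in LR are covered by the rule.
- The range of 8 to 12 weeks is not a general figure. It belongs to two or three missed 4-weekly assessments. Two missed odd-cycle visits from Cycle 25 give 20 weeks.
- Death does not differ from LR by a fixed amount, and keeping its observed date is not in itself an error.

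The conclusion rests on reading Table 2 literally and on the nominal visit schedule.

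**What to change.** Reword the rule in SAP Table 2 along these lines:

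> *If deterioration from best response (including CR to PR), LR, or initiation of new systemic therapy follows two or more consecutive missed scheduled clinic response assessments, the event date is the date of the first missed scheduled clinic assessment. From Cycle 25, even-cycle contacts without a clinic visit are not scheduled assessments.*

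Each DOR definition applies this to its own listed events, so CR-to-PR enters only primary DOR. For death after such a gap, state whether the observed date is kept. If it is, add a sensitivity analysis that applies the same dating rule to deaths.

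The cost is a small change in wording and programming. Some primary DOR values become shorter (CR-to-PR after a gap), and a few late ones become longer (after Cycle 25, last+8 instead of last+4).

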### 3.8.2.2 Time-to-Response (TTR)

Time-to-response will be measured as the time from first treatment to the time of first documentation of response. Descriptive statistics and plots of cumulative number and percent of responders over time (at 4, 8, 12, 16, 24, 32, 40, and  $\geq 48$  weeks) will be provided. The TTR analyses will only be conducted for the Responder Population.

### 3.8.2.3 Response by Organ System

The database did not specifically capture baseline organ involvement. Organ involvement was determined as follows:

- All organs, except lungs:
  - If the baseline score is  $> 0$ , the organ will be defined as Involved, unless all response assessments are Not Evaluable (NE)
  - If the baseline score is 0, the organ will be defined as Not Involved, unless any response assessment of CR or PR which triggers clinical review to confirm baseline involvement.
- For the lungs:
  - If FEV1  $\geq 75\%$ , the organ will be defined as Not Involved
  - If FEV1  $< 75\%$ , the organ will be defined as Involved, unless all responses are NE

The response assessment for the 9 individual organs (skin, eyes, mouth, esophagus, upper GI, lower GI, liver, lungs, and joints and fascia) and global severity rating is categorized into 5 response status: CR, PR, Progression (P), NE, Stable (STB).

Number and percentage of subjects with best response of CR or PR and total (CR+PR) by individual organ system and global severity rating will be summarized and 2 series of percentages presented:

1. With the total number of subjects in the mITT Population with involvement of the given organ at baseline as denominator
2. With the number of subjects in the Responder Population with involvement of the given organ at baseline as denominator

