**Appendix B: cGVHD Response Assessment**

Response Determination for Chronic GVHD Clinical Trials based on Clinician Assessments

Organ	Complete Response	Partial Response	Progression
Skin	NIH Skin Score 0 after previous involvement	Decrease in NIH Skin Score by 1 or more points	Increase in NIH Skin Score by 1 or more points, except 0 to 1
Eyes	NIH Eye Score 0 after previous involvement	Decrease in NIH Eye Score by 1 or more points	Increase in NIH Eye Score by 1 or more points, except 0 to 1
Mouth	NIH Modified OMRS 0 after previous involvement	Decrease in NIH Modified OMRS of 2 or more points	Increase in NIH Modified OMRS of 2 or more points
Esophagus	NIH Esophagus Score 0 after previous involvement	Decrease in NIH Esophagus Score by 1 or more points	Increase in NIH Esophagus Score by 1 or more points, except 0 to 1
Upper GI	NIH Upper GI Score 0 after previous involvement	Decrease in NIH Upper GI Score by 1 or more points	Increase in NIH Upper GI Score by 1 or more points, except 0 to 1
Lower GI	NIH Lower GI Score 0 after previous involvement	Decrease in NIH Lower GI Score by 1 or more points	Increase in NIH Lower GI Score by 1 or more points, except from 0 to 1
Liver	Normal ALT, alkaline phosphatase, and Total bilirubin after previous elevation of 1 or more	Decrease by 50%	Increase by 2 × ULN
Lungs	- Normal %FEV1 after previous involvement - If PFTs not available, NIH Lung Symptom Score 0 after previous involvement	- Increase by 10% predicted absolute value of %FEV1 - If PFTs not available, decrease in NIH Lung Symptom Score by 1 or more points	- Decrease by 10% predicted absolute value of %FEV1 - If PFTs not available, increase in NIH Lung Symptom Score by 1 or more points, except 0 to 1
Joints and fascia	Both NIH Joint and Fascia Score 0 and P-ROM score 25 after previous involvement by at least 1 measure	Decrease in NIH Joint and Fascia Score by 1 or more points or increase in P-ROM score by 1 point for any site	Increase in NIH Joint and Fascia Score by 1 or more points or decrease in P-ROM score by 1 point for any site
Global	Clinician overall severity score 0	Clinician overall severity score decreases by 2 or more points on a 0-10 scale	Clinician overall severity score increases by 2 or more points on a 0-10 scale

ULN indicates upper limit of normal.

Abstracted from: Lee SJ, Wolff D, Kitko C, et al. *Biol Blood Marrow Transplant* 2015; 21:984 – 999.

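### SAP 3.8.2.3 lets post-baseline results help decide which organs count as involved at baseline, through never-evaluable organs and through joints and fascia scored 0

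*SAP*

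**What the plan says.** SAP 3.8.2.3 explains why a rule is needed: "The database did not specifically capture baseline organ involvement". Involvement is therefore derived, and the derived status sets both denominators for organ response (mITT subjects and responders with the organ involved at baseline).

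- **Every organ except lungs, baseline score above 0:** "the organ will be defined as Involved, unless all response assessments are Not Evaluable (NE").
- **Every organ except lungs, baseline score 0:** "the organ will be defined as Not Involved, unless any response assessment of CR or PR which triggers clinical review to confirm baseline involvement".
- **Lungs:** FEV1 of 75% or more is not involved. Below 75%, "the organ will be defined as Involved, unless all responses are NE".

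Two other places bear on these rules. For the primary endpoint, SAP 3.8.1 states: "If a treated subject does not have any response assessment, this subject will be counted as a non-responder". For joints and fascia, SAP Appendix B defines complete response as "Both NIH Joint and Fascia Score 0 and P-ROM score 25 after previous involvement by at least 1 measure" and partial response as "Decrease in NIH Joint and Fascia Score by 1 or more points or increase in P-ROM score by 1 point for any site". It thus recognises two routes to involvement, and it accepts a response on P-ROM alone.

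**The concern.** A denominator described as baseline involvement should be fixed by what was known at baseline. Two branches of this rule depend on what happened afterwards.

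1. **Joints and fascia.** Suppose the baseline score in the rule is the NIH Joint and Fascia Score. A subject with score 0 but P-ROM below 25 is then looked at again only if a CR or PR is recorded. If review confirms involvement, that subject enters numerator and denominator together. A subject with the same baseline findings who does not respond is never reviewed and never enters.
2. **Never-evaluable organs.** An organ that met the baseline criterion leaves the denominator if every later assessment is NE. Such an organ cannot be a responder, so only non-responders leave by this route. The SAP expands the abbreviation NE but does not define when it applies. It also does not say whether an organ with no later assessment counts as all NE.

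The organ tables are planned for the mITT and Responder populations and by cohort of about 16 (SAP 3.1.2 and Tables 1 and 5). With so few subjects per organ, moving one is visible in the percentage.

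**Working it through.** The documents give no figure for organ response, so there is nothing to reproduce. The rules come from SAP 3.8.2.3 and Appendix B. **All counts below are assumptions** chosen to show direction and scale.

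**Never-evaluable organs.** Let N organs meet the baseline criterion, R respond, and a be NE throughout.

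- Kept as non-responders: R/N.
- SAP rule: R/(N − a).
- Since a ≥ 0 and N − a > 0, R/(N − a) is never below R/N.

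N = 20, R = 8: 8/20 = 40.0% becomes 8/19 = 42.1%, 8/18 = 44.4% or 8/17 = 47.1% with a = 1, 2 or 3.

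N = 6, R = 2 (one organ in one cohort): 2/6 = 33.3% becomes 2/5 = 40.0% or 2/4 = 50.0% with a = 1 or 2.

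**Joints and fascia.** Let N subjects have NIH score above 0, with R responding. Let m have score 0 but P-ROM below 25, with b of those responding.

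- Everyone classified at baseline by either measure: (R + b)/(N + m).
- SAP rule with all b confirmed on review: (R + b)/(N + b).
- SAP rule with none confirmed: R/N.
- Since b ≤ m, the second rate is never below the first. They are equal when b = m.

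With N = 10, R = 4, m = 4:

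| b | Baseline classification | SAP, all confirmed | Difference (points) | SAP, none confirmed |
|---|---|---|---|---|
| 0 | 4/14 = 28.6% | 4/10 = 40.0% | +11.4 | 40.0% |
| 1 | 5/14 = 35.7% | 5/11 = 45.5% | +9.7 | 40.0% |
| 2 | 6/14 = 42.9% | 6/12 = 50.0% | +7.1 | 40.0% |
| 3 | 7/14 = 50.0% | 7/13 = 53.8% | +3.8 | 40.0% |
| 4 | 8/14 = 57.1% | 8/14 = 57.1% | 0 | 40.0% |

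The last column shows that the direction depends on the review. If none is confirmed, the SAP rate falls below the baseline-classified rate once b is 2 or more.

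**Which organs the score-0 branch reaches.** Skin, eyes, mouth, esophagus, upper GI and lower GI are judged on an NIH score or the OMRS alone. None can improve from 0, so a CR or PR there is essentially a data query. Lungs have no such branch. Joints and fascia are the clear case. Reading the baseline score to include P-ROM does not repair the rule: Appendix B requires P-ROM 25 for complete response, so a criterion of above 0 would count subjects at that value as involved.

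**The case against.** **The never-evaluable rule follows the plan's own default.** SAP 3.1.5 leaves subjects with missing data out of percentages unless otherwise specified, and Protocol 17.1 excludes a subject who lacks sufficient data for an analysis. SAP 3.8.1 is an explicit exception for the primary endpoint, and it covers a subject with no response assessment at all, whereas NE is one of five recorded organ statuses. This stands. A reader might infer that 3.8.2.3 and 3.8.1 contradict each other, but they are two conventions for two endpoints. What remains is that the default justifies an evaluable-only percentage. It does not justify redefining who was involved at baseline.

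**An all-NE organ may never have been GVHD.** Form A (SAP Appendix A) lets the clinician record an abnormality explained entirely by another cause. Counting such organs as failures could push rates down. In the Responder denominator every subject had at least one overall CR or PR, so a complete lack of assessments cannot explain an all-NE organ there. This also stands. A reader might infer that organ rates are biased upward against true involvement. The documents do not support that, because true involvement was not captured and nothing links NE to outcome. The rule does not, however, require a non-GVHD cause before an organ is dropped.

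**A response at score 0 triggers review; it does not reclassify.** True, and if review confirms no one the joint rate can be too low. The asymmetry remains, because non-responders are never reviewed.

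**The listing allows recomputation.** SAP Table 5 plans organ scores and responses by subject and visit. That helps a reader but leaves the tables as they are.

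**Conclusion.** The concern holds in a limited form: a denominator described as baseline involvement depends partly on later results.

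- **Joints and fascia:** the reported rate is higher than, or equal to, the rate with everyone classified at baseline, provided that the baseline score means the NIH Joint and Fascia Score and that review confirms the responders. In the example the gap runs from 0 to 11.4 points.
- **Never-evaluable organs:** relative to keeping them as non-responders, the rule can only raise an organ rate or leave it unchanged. Bias against true GVHD involvement is possible but not shown.

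The real counts are unknown and the effect may be zero. The endpoint is secondary and descriptive, with no test attached, so severity is minor to moderate.

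Three wider readings are not supported. The primary ORR does not use this flag, so it is not affected. The subgroup of fewer than 4 versus 4 or more organs is affected only if it uses the same derivation, which SAP 3.8.4 does not say. The liver denominator is not shown to be biased: 3.8.2.3 gives no usable cut for organs measured by laboratory values, but Appendix B implies one through "Normal ALT, alkaline phosphatase, and Total bilirubin after previous elevation of 1 or more", so the liver needs only a clarification.

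**What to change.** Set involvement from baseline data only:

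- Scored organs: score above 0.
- Joints and fascia: NIH score above 0 or P-ROM below 25.
- Lungs: the existing FEV1 cut, with a statement of what happens when baseline FEV1 is missing, since Appendix B falls back on the lung symptom score.
- Liver, as a clarification: at least one of ALT, ALP or total bilirubin above ULN, as Appendix B implies.

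Define NE, and say how an organ with no later assessment is handled. Report each organ rate twice: with all-NE organs kept as non-responders, and on evaluable organs only. Treat a CR or PR recorded from score 0 in the other scored organs as a data query. Apply any review of baseline involvement regardless of later response. Use the Form A box to exclude non-GVHD abnormalities only if it was captured in the database. State in SAP 3.8.4 that the organ-count subgroup uses the same definition.

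The cost is SAP wording and light programming. Baseline P-ROM and liver values are already planned for summary (SAP 3.5.3). Any review of involvement must go back to source records, and keeping reviewers unaware of response takes some effort in an open-label study. Reported organ response rates may be slightly lower.
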